8.2.5.8. Preexisting Medical Conditions

A preexisting medical condition is one that is present at the Screening visit for this study. Such conditions should be recorded on the Medical History CRF.

A preexisting medical condition should be recorded as an AE only if the frequency, severity, or character of the condition worsens during the study. When recording such events on the Adverse Event CRF, it is important to convey the concept that the preexisting condition has changed by including applicable descriptors (e.g., "worsening headaches").

8.2.5.9. Lack of Efficacy or Worsening of the Malignancy Under Study

Events that are clearly consistent with the expected pattern of progression of the underlying disease should not be recorded as AEs. These data will be captured as efficacy assessment data only. In most cases, the expected pattern of progression will be reflected as objective radiographic progression according to RECIST v 1.1 criteria. In rare cases, the determination of disease progression will be based predominantly on symptomatic deterioration. However, every effort should be made to document progression through use of objective criteria. If there is any uncertainty as to whether an event is due to disease progression, it should be reported as an AE.

8.2.5.10. Hospitalization or Prolonged Hospitalization

Any AE that results in hospitalization (i.e., in-patient admission to a hospital) or prolonged hospitalization should be documented and reported as a SAE, except as outlined below.

The following hospitalization scenarios are not considered to be AEs:

- Hospitalization for respite care or social admissions (e.g., lack of housing, economic inadequacy, family circumstances)
- Hospitalization solely for coordination of care, including hospice arrangements
- Hospitalization due solely to progression of the underlying cancer
- Hospitalization that was necessary solely because of subject requirement for outpatient care outside of normal outpatient clinic operating hours
- Hospitalization for same day surgeries (as outpatient/same day/ambulatory procedures)
- Planned hospitalization required by the protocol (e.g., for study drug administration or insertion of access device for study drug administration)
- Hospitalization for a preexisting condition, provided that the hospitalization was planned prior to the study or was scheduled during the study when elective surgery became necessary because of the expected normal progression of the disease and the subject has not experienced an AE

8.2.5.11. Exposure During Pregnancy

For investigational products and for marketed products, an exposure during pregnancy occurs if:

- A female becomes, or is found to be, pregnant either while receiving or having been exposed (e.g., because of treatment or environmental exposure) to the investigational

product; or the female becomes, or is found to be pregnant after discontinuing and/or being exposed to the investigational product. An example of environmental exposure would be a case involving direct contact with investigational product in a pregnant woman (e.g., a nurse reports that she is pregnant and has been exposed to chemotherapeutic products).

- A male subject has been exposed (e.g., because of treatment or environmental exposure) to the investigational product prior to or around the time of conception and/or is exposed during his partner's pregnancy.

If a study subject or study subject's partner becomes or is found to be pregnant during the study subject's treatment with the investigational product, the Investigator must submit this information to Premier Research Pharmacovigilance (Premier PV) on a SAE Report Form (if applicable) and Pregnancy Data Collection Form. In addition, the Investigator must submit information regarding environmental exposure to an investigational product in a pregnant woman (e.g., a subject reports that she is pregnant and has been exposed to a cytotoxic product by inhalation or spillage). This must be done irrespective of whether an AE has occurred and within 24 hours of awareness of the exposure. The information submitted should include the anticipated date of delivery (see below for information related to termination of pregnancy).

Follow-up is conducted to obtain general information on the pregnancy and its outcome for all Pregnancy Data Collection Forms with an unknown outcome. The Investigator will follow the pregnancy until completion or until pregnancy termination and notify Premier PV of the outcome as a follow-up to the initial Pregnancy Data Collection Form. In the case of a live birth, the structural integrity of the neonate can be assessed at the time of birth. In the event of a termination, the reason(s) for the termination should be specified and, if clinically possible, the structural integrity of the terminated fetus should be assessed by gross visual inspection (unless pre-procedure test findings are conclusive for a congenital anomaly and the findings are reported).

If the outcome of the pregnancy meets the criteria for an SAE (i.e., ectopic pregnancy, spontaneous abortion, intrauterine fetal demise, neonatal death, or congenital anomaly [in a live born, a terminated fetus, an intrauterine fetal demise or a neonatal death]), the Investigator should follow the procedures for reporting SAEs.

Additional information about pregnancy outcomes that are reported as SAEs follows:

- Spontaneous abortion includes miscarriage and missed abortion.
- Neonatal deaths that occur within 1 month of birth should be reported, without regard to causality, as SAEs. In addition, infant deaths after 1 month should be reported as SAEs when the Investigator assesses the infant death as related or possibly related to exposure to investigational product.

Additional information regarding the exposure during pregnancy may be requested by the Investigator. Further follow-up of birth outcomes will be handled on a case-by-case basis (e.g., follow-up on preterm infants to identify developmental delays). In the case of paternal exposure, the Investigator will provide the study subject with the pregnant partner release of information form to deliver to his partner. The Investigator must document in the source

documents that the subject was given the pregnant partner release of information form to provide to his pregnant partner.

8.2.5.12. Occupational Exposure

An occupational exposure occurs when during the performance of job duties, a person (whether a healthcare professional or otherwise) has unplanned direct contact with the product, which may or may not lead to the occurrence of an AE.

An occupational exposure is reported to safety within 24 hours of Investigator's awareness, using the SAE Report Form, regardless of whether there is an associated AE/SAE. Since the information does not pertain to a subject enrolled in the study, the information is not reported on a CRF, however a copy of the completed SAE Report Form is maintained in the study master file.

8.2.5.13. Adverse Events Associated with an Overdose or Incorrect Administration of Study Drug

An overdose is the accidental or intentional use of a drug in an amount higher than the dose being studied. An overdose or incorrect administration of study treatment is not itself an AE, but it may result in an AE. All AEs associated with an overdose or incorrect administration of study drug should be recorded on the Adverse Event CRF. If the associated AE fulfills serious criteria, the event should be reported to Turning Point Therapeutics Medical Monitor immediately (i.e., no more than 24 hours after learning of the event).

8.3. Immediate Reporting Requirements from Investigator to Turning Point Therapeutics

Certain events require immediate reporting to allow Turning Point Therapeutics to take appropriate measures to address potential new risks in a clinical trial. The Investigator must report such events to Turning Point Therapeutics immediately; under no circumstances should reporting take place more than 24 hours after the Investigator learns of the event. The following is a list of events that the Investigator must report to Turning Point Therapeutics within 24 hours after learning of the event, regardless of relationship to study drug:

- Serious AE (whether or not deemed drug-related or expected).
- Pregnancy of female subject or partner of male subject of childbearing potential.
- Occupational Exposure (regardless of whether there is an associated AE/SAE)

The Investigator must report new significant follow-up information for these events to Premier Research GPV immediately (i.e., no more than 24 hours after becoming aware of the information). New significant information includes the following:

- New signs or symptoms or a change in the diagnosis
- Significant new diagnostic test results
- Change in causality based on new information
- Change in the event's outcome, including recovery

- Additional narrative information on the clinical course of the event

Investigators must also comply with local requirements for reporting SAEs to the local health authority and IRB/EC.

8.3.1. SAE Reporting

After informed consent has been obtained but prior to initiation of study drug, only SAEs related to protocol-mandated procedures should be reported.

After initiation of study drug, SAEs will be reported until at least 28 days after the last dose of study drug.

Investigators should record all case details that can be gathered immediately (i.e., within 24 hours after learning of the event) on the SAE Report Form and submit the report via fax or email (please refer to the Study Manual).

8.3.2. Immediate Reporting Requirements for Pregnancies

8.3.2.1. Pregnancies in Female Subjects

Female subjects or partners of male subjects of childbearing potential will be instructed to immediately inform the Investigator if they become pregnant during the study or within 4 months after the last dose of study drug. A Pregnancy Data Collection Form should be completed by the Investigator no more than 24 hours after learning of the pregnancy and submitted using the same process as for SAEs. Refer to [Section 8.2.5.11](#) for further information on reporting requirements for exposure during pregnancy.

The Investigator should discontinue study drug and counsel the subject or partner of a male subject, discussing the risks of the pregnancy and the possible effects on the fetus. Monitoring should continue until conclusion of the pregnancy. Any SAEs associated with the pregnancy (e.g., an event in the fetus, an event in the mother during or after the pregnancy, or a congenital anomaly/birth defect in the child) should be reported and submitted within 24 hours. Refer to [Section 8.2.5.11](#) for additional information regarding follow-up and SAE reporting requirements for exposure during pregnancy.

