Abbreviations: KRAS = Kirsten rat sarcoma viral oncogene homolog; MEK = mitogen-activated protein kinase; NSCLC = non-small cell lung cancer; RP2D = recommended Phase 2 dose.

Phase 1b Dose Escalation

Subjects with locally advanced or metastatic solid tumor malignancies harboring a *KRAS*^{G12D} mutation will be enrolled into the Phase 1b dose escalation portion of the study to determine the MTD/RP2D of repotrectinib in combination with trametinib. Dose escalation will follow a traditional 3+3 design.

Phase 2 Expansion

Once the MTD/RP2D of repotrectinib in combination with trametinib has been determined, subjects will be enrolled into a Phase 2 expansion portion. The Phase 2 portion is designed to explore the anti-tumor efficacy and safety of repotrectinib in combination with trametinib for the treatment of patients with locally advanced or metastatic NSCLC harboring a *KRAS*^{G12D} mutation.

Treatment Duration

Subjects may receive treatment with repotrectinib in combination with trametinib until disease progression or unacceptable toxicity. Subjects may continue treatment with single agent repotrectinib or trametinib if there is continuing clinical benefit per Investigator's judgment and in consultation with the Sponsor's Medical Monitor. After discontinuation of both study drugs, subjects will continue to be followed on study for overall survival.

Phase 1b Dose Escalation Study Design:

Subjects with locally advanced or metastatic solid tumor malignancies harboring a *KRAS*^{G12D} mutation will be enrolled into the Phase 1b dose escalation portion of the study to determine the MTD/RP2D of repotrectinib in combination with trametinib. Initially, approximately 24 – 30 subjects with locally advanced or metastatic solid tumor malignancies harboring a *KRAS*^{G12D} mutation will be enrolled.

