Abbreviations: AST/ALT = aspartate aminotransferase/alanine aminotransferase, ULN = upper limit of normal.

* calculated by Cockcroft and Gault's formula: $(140 - \text{age [yr.]}) \times \text{body weight [kg]} \times 1.23 \times (0.85 \text{ if female}) / \text{serum creatinine [\mu mol/L]}$.

9. Women of childbearing potential (WOCBP) must have a negative serum pregnancy test during screening and be neither breastfeeding nor intending to become pregnant during study participation. Female patients will be considered to be of childbearing potential unless they have undergone permanent sterilization or are postmenopausal. Postmenopausal is defined as at least 12 months without menses with no other medical reasons (e.g., chemical menopause due to anticancer treatment). For WOCBP and for men, agreement to use a highly effective contraceptive method from the time of screening throughout the study until 4 months (WOCBP) or 6 months (men) after administration of the last dose of any study drug. Highly effective contraceptive methods consist of prior sterilization, intrauterine device (IUD), intrauterine hormone-releasing system (IUS), injectable or implantable contraceptives. All male study subjects must agree to use condoms throughout the study and 6 months after administration of the last dose. Male partners of WOCBP subjects must agree to condom use throughout the study and for 4 months following the last dose of study drug. True abstinence is acceptable if evaluated as consistent with the preferred and the usual lifestyle of the subject. Periodic abstinence is not an acceptable method of contraception.
10. Ability to swallow capsules and tablets intact (without chewing, crushing, or opening).
11. Life expectancy ≥ 3 months.
12. Willingness and ability to comply with scheduled visits, treatment plan, laboratory tests, and other study procedures.

Additional Inclusion Criteria for Phase 1 only:

13. Subject must have received prior standard therapy appropriate for their tumor type and stage of disease, or in the opinion of the Investigator, would be unlikely to tolerate or derive clinically meaningful benefit from appropriate standard of care therapy.
 - Subject must have received no more than 3 prior systemic regimens.
 - Maintenance therapy will not be counted as a separate regimen.

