9. Women of childbearing potential (WOCBP) must have a negative serum pregnancy test during screening and be neither breastfeeding nor intending to become pregnant during study participation. Female patients will be considered to be of childbearing potential unless they have undergone permanent sterilization or are postmenopausal. Postmenopausal is defined as at least 12 months without menses with no other medical reasons (e.g., chemical menopause due to anticancer treatment). For WOCBP and for men, agreement to use a highly effective contraceptive method from the time of screening throughout the study until 4 months (WOCBP) or 6 months (men) after administration of the last dose of any study drug. Highly effective contraceptive methods consist of prior sterilization, intrauterine device (IUD), intrauterine hormone-releasing system (IUS), injectable or implantable contraceptives. All male study subjects must agree to use condoms throughout the study and 6 months after administration of the last dose. Male partners of WOCBP subjects must agree to condom use throughout the study and for 4 months following the last dose of study drug. True abstinence is acceptable if evaluated as consistent with the preferred and the usual lifestyle of the subject. Periodic abstinence is not an acceptable method of contraception.

10. Ability to swallow capsules and tablets intact (without chewing, crushing, or opening).
11. Life expectancy ≥ 3 months.
12. Willingness and ability to comply with scheduled visits, treatment plan, laboratory tests, and other study procedures.

Additional Inclusion Criteria for Phase 1 Only:

13. Subject must have received prior standard therapy appropriate for their tumor type and stage of disease, or in the opinion of the Investigator, would be unlikely to tolerate or derive clinically meaningful benefit from appropriate standard of care therapy.
 - Subject must have received no more than 3 prior systemic regimens.
 - Maintenance therapy will not be counted as a separate regimen.
 - Adjuvant chemotherapy or chemotherapy administered as part of concurrent chemotherapy and radiation therapy will not count as a prior regimen of systemic

therapy as long as recurrence occurred more than 6 months after the last day of chemotherapy.

Additional Inclusion Criteria for Phase 2 Only:

14. Histologically or cytologically confirmed diagnosis of advanced or metastatic NSCLC harboring a *KRAS*^{G12D} mutation.

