7.8.5. Contraception

Women of childbearing potential (WOCBP) must have a negative serum pregnancy test during Screening and be neither breast feeding nor intending to become pregnant during study participation. A female will be considered to be of childbearing potential unless they have undergone permanent sterilization or are postmenopausal. Postmenopausal is defined as at least 12 months without menses with no other medical reasons (e.g., chemical menopause due to anticancer treatment).

For WOCBP, agreement must be provided to use a highly effective contraceptive method from the time of screening throughout the study until 4 months (WOCBP) after administration of the last dose of any study drug. Highly effective methods of contraception are those that, alone or in combination, result in a failure rate of less than 1% per year when used consistently and correctly (i.e., perfect use) and include the following:

- Established use of combined (estrogen and progestogen containing) hormonal methods of contraception (intravaginal, or transdermal) provided the subject remains on the same treatment throughout the entire study and has been using that hormonal contraceptive for an adequate period of time to ensure inhibition of ovulation.
- Progestogen-only hormonal contraception (injectable, or implantable) provided the subject remains on the same treatment throughout the entire study and has been using that hormonal contraceptive for an adequate period of time to ensure inhibition of ovulation.
- Correctly placed copper containing intrauterine device (IUD).
- Intrauterine hormone-releasing system (IUS).
- Vasectomized partner with appropriately confirmed absence of sperm in the post-vasectomy ejaculate.
- Bilateral tubal ligation or bilateral salpingectomy.
- Sexual abstinence is acceptable if evaluated as consistent with the preferred and the usual lifestyle of the subject. Periodic abstinence is not an acceptable method of contraception.

All male study subjects must agree to condom use throughout the study and for 6 months following the last dose of study drug. Male partners of WOCBP subjects must agree to condom use throughout the study and for 4 months following the last dose of study drug.

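### The 4-month post-dose pregnancy-notification limit in Section 8.3.2.1 is 2 months shorter than the 6-month precaution period for male subjects

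*Combined protocol and SAP*

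**What the plan says.** Section 8.3.2.1 is headed for pregnancies in female subjects, but its first sentence also covers partners of male subjects. Both groups are to notify "if they become pregnant during the study or within 4 months after the last dose of study drug". The Investigator's own step follows from that: "A Pregnancy Data Collection Form should be completed by the Investigator no more than 24 hours after learning of the pregnancy".

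The precaution periods differ by sex. Inclusion criterion 9 in Section 4.1 requires contraception "throughout the study until 4 months (WOCBP) or 6 months (men) after administration of the last dose of any study drug". Section 7.8.5 says: "All male study subjects must agree to condom use throughout the study and for 6 months following the last dose of study drug". The Synopsis version of criterion 9 agrees: "All male study subjects must agree to use condoms throughout the study and 6 months after administration of the last dose". The other 4-month condom period in Section 7.8.5 belongs to a different group: "Male partners of WOCBP subjects must agree to condom use throughout the study and for 4 months following the last dose of study drug".

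Two further statements bear on the point. Section 8.3 lists, among events to be reported within 24 hours of the Investigator learning of them, "Pregnancy of female subject or partner of male subject of childbearing potential", with no post-dose limit. The Synopsis, under Treatment Duration, says: "After discontinuation of both study drugs, subjects will continue to be followed on study for overall survival".

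**The concern.** The protocol treats the 6 months after a man's last dose as a period in which conception should be avoided. A partner's pregnancy beginning more than 4 and up to 6 months after that dose lies inside this period but outside the explicit notification limit.

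The Investigator's duty starts only once the pregnancy is known. Female subjects of childbearing potential have scheduled pregnancy tests through the Safety Follow-up visit (Table 1). Partners have no study visits or tests. After treatment, the planned contacts with male subjects are survival status every 3 months (Sections 3.2 and 7.7) or continued tumor assessments for those who stop before progression (Section 7.4). None of these sections lists a question about pregnancy. In the text reviewed, the instruction in Section 8.3.2.1 is therefore the stated route by which a late partner pregnancy reaches the site. What is at stake is the completeness of pregnancy data after paternal exposure.

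**Working it through.** The 4-month limit is a stated rule and not a computed figure, so there is nothing to reproduce. The check compares periods and then asks which reading of the sentence applies.

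**Inputs**
- Notification limit after last dose, both groups: 4 months (Section 8.3.2.1).
- Contraception period, women of childbearing potential: 4 months (Section 4.1, criterion 9).
- Contraception period, male subjects: 6 months (Section 4.1, criterion 9; Section 7.8.5; Synopsis).

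**Step 1: shortfall of the explicit limit** = contraception period − notification limit.
- Female subjects: 4 − 4 = 0 months.
- Partners of male subjects: 6 − 4 = 2 months; 2/6 = 33% of the precaution period.

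**Step 2: practical gap for partners.** The sentence joins two conditions with *or*, so coverage runs to whichever ends later. If the male subject's time on study ends L months after his last dose, the instruction covers the partner to max(L, 4) months, and the gap is 6 − max(L, 4), with a floor of 0.
- Study ends with treatment (L = 0): 6 − 4 = 2 months.
- Follow-up counts as study, and he leaves by month 4: 6 − 4 = 2 months.
- Follow-up counts as study, and he leaves at month 5 (illustration): 6 − 5 = 1 month.
- Follow-up counts as study, and he stays to month 6 or later: 0 months.

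**Step 3: which reading the text favors.**
- *Survival follow-up is part of the study.* The Synopsis describes survival follow-up as taking place on study. Section 7.6 treats follow-up as a part of the study. Section 7.5 separates stopping the drug from later study follow-up. Section 6.12 lets a pregnant subject stop the drug yet stay in the study.
- *The study ends with treatment.* Criterion 9 and Section 7.8.5 pair the whole study with a number of months after the last dose, which reads most naturally if the study ends at that dose. Section 8.5 uses a post-study label for events later than 28 days after the last dose.

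Usage is not uniform. The statements that directly describe follow-up favor the first reading; the second is inferred from phrasing.

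**Step 4: whether another section supplies the missing 2 months.** Section 8.3 gives no window and begins with the Investigator's knowledge. The form-submission sentence in Section 8.2.5.11 concerns pregnancy arising during the subject's treatment, although the same section counts paternal exposure before or around conception as an exposure. Section 8.3.2.2 concerns congenital anomalies and abortions. None gives partners a 6-month notification window.

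**The case against.** The strongest reply is that there may be no gap at all. If survival follow-up is part of the study, a man still in follow-up is covered through month 6 and beyond, and the site is still in contact with him. The 4-month limit is not idle on that reading, because it serves those who leave early. This stands, and it is why the practical gap is given as a range starting at 0. It does not change the fact that the one explicit number for partners is the women's number, or that men who leave before month 6 have less cover. For a man who withdraws consent to further contact, Section 7.6 stops data collection, so a longer limit may add little for him.

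A second reply is that the Investigator must report any partner pregnancy that becomes known, however late, and must complete the form within 24 hours. This also stands. A reader might infer that partner pregnancies in months 5 and 6 need not be reported; Sections 8.3 and 8.3.2.1 do not support that. Only the instruction that brings the pregnancy to the Investigator's attention is limited.

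A third reply is that nothing in the protocol requires the notification and contraception windows to match. That is so, but the 6 months is the protocol's own judgment of the period of concern for men, and no reason is given for a shorter notification limit.

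A reader might also infer that subjects are being told 4 months. Consent pages are not in the text reviewed, so that cannot be determined.

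**Conclusion.** The explicit post-dose limit is 2 months short for partners of male subjects (4 against 6) and exact for female subjects (4 against 4). The practical gap is 0 months while a male subject remains in survival follow-up, provided that follow-up counts as part of the study. It is up to 2 months if the study ends with treatment or he leaves before month 6.

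A definite 2-month hole in pregnancy reporting would be too strong a conclusion: the Synopsis and Section 7.6 support the broader reading of the study, and Section 8.3 sets no end date once a pregnancy is known. The documents give no basis for estimating how many pregnancies could be involved. This is a minor safety-reporting inconsistency, with no effect on the response-rate analysis, the sample size or the futility rule.

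**What to change.** In the first sentence of Section 8.3.2.1, keep the words *during the study* and change only the post-dose limit, from 4 months for everyone to *4 months (female subjects) or 6 months (partners of male subjects)*. This matches criterion 9 and Section 7.8.5.

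The reference to the study should not be narrowed to study treatment. That would settle the ambiguity but, on the broader reading, would shorten an instruction that now runs through survival follow-up.

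The cost is a few words in one sentence, with no added visits, procedures or analyses. Aligning the form-submission sentence in Section 8.2.5.11 is optional, since Sections 8.3 and 8.3.2.1 already require the report and the form once a pregnancy is known.
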